**C.2.5 Sample size estimation.** We conservatively estimated the minimal detectable difference between treatment arms to be 0.4 to 0.6 standard deviations for our target sample size of 60 per group (after attrition) at the 12-week post-treatment measurement based on a 2-groups pre-post design,  $\alpha = 0.02$ , 2-sided, and 80% power. This represents a modest but clinically important change. Table 4 shows projected estimates for attention controls, based on our pilot data with this population, and the treatment group, based on the minimum detectable difference we could detect as statistically significant given our design, target sample size, and correlations between time points of 0.5 to 0.8. Standard deviations from pilot data for A1C (1.07%), sleep

variability (30 minutes), and sleep duration (49 minutes), and the correlation between measurements ( $r = 0.56$  to 0.85) were used for sample size determination.

Table 4. Minimum detectable treatment effects		
	Control	Treatment
A1C (%)	7.8	7.4
Sleep variability (minutes)	75	57
Sleep duration (minutes)	355	380

Analyses adjusting for the pre-treatment glucose level and other key covariates (e.g., BMI) will increase power. Aim 2 assesses the main effects of secondary outcomes and, similar to the primary aim, will allow us to detect effect sizes of 0.3 to 0.5 or greater as statistically significant. **Adjustment for multiple testing.** Our primary aim uses an adjusted alpha level for multiple primary outcomes. For secondary aims, exploratory, and hypothesis generating analyses we will publish unadjusted p-values and apply

the Benjamini-Hochberg approach to control the family-wise error rate. Aim 3 pertains to correlations between change measures of sleep and glucose control parameters, for which we will be able to detect correlations of the magnitude of .25 or greater as statistically significant.

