During the first video conference we will meet for approximately one hour to review the study procedures and instruct a subject how to use the study materials (pregnancy test strips, measurement tape, CGM (FreeStyle Libre Pro CGM and Reader or Dexcom), Actiwatch, A1C kit, paper sleep log, postage-paid package to return supplies). If applicable, (1) a subject (women) will test urine for pregnancy; (2) measure their waist circumference using a measurement tape; and (3) provide eGFR and most recent height and weight from health provider. Then subjects will wear (1) a continuous glucose monitor (CGM) and (2) Actiwatch (3) fill out paper sleep log for one week. The CGM is placed under the skin on their arm using sterile technique. Subjects will be provided instructions on how to care for the CGM. They will also be given an Actiwatch to track their sleep for one week. After one week of wearing the CGM and Actiwatch, subject will remove the CGM and Actiwatch and return them in the mail using the postage-paid package. In addition, subjects will use fingerstick blood sampling to obtain measures of A1C. Following the 1-week run-in period and a confirmation of sleep variability ( $\geq 1$  hr) or mean sleep duration ( $< 6.5$  h/night) during work- or weekdays, A1C results, and other inclusion criteria, subjects will be randomly assigned to the Sleep-Opt intervention or Healthy Living attention control group. We will use permuted blocks of 4, arranged in random order and stratified by sex, A1C and age. The use of permuted blocks preserves balance in randomization over the course of the study (i.e., at any point in time, there will be approximately equal numbers of patients randomized to the intervention or attention control group). The randomization model will be developed by the study statistician ([name]) and executed through the Research Data Capture (REDCap) data management system. Investigators overseeing intervention and control groups and project director are unblinded; for all other investigators and key personnel, randomization allocation will be concealed through blinded coding within REDCap. During the study period, subjects will continue to receive their usual diabetes care with their health care provider and care for their diabetes as they normally would.

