## C.2.10 Data Analysis

### Statistical Analysis

We will conduct descriptive analyses of measured variables, evaluate associations among variables, and changes over time. This review of the data will allow us to identify covariates (e.g. age groups, treatment regimen) that may require statistical adjustment in the final models. We will conduct exploratory analyses with baseline cross-sectional data using our de-identified data which may include emerging approaches to capture and analyze sleep and glucose metrics in this rapidly evolving area of research.

Our *overall statistical approach* will be a mixed-effect model for repeated measures (MMRM), recommended for primary analysis of clinical trials with continuous endpoints. Conceptually, MMRM is a more advanced version of repeated-measures ANOVA that can account for the correlation among multiple measurements over time, yet there is no assumption that participants are measured at every time point. Therefore, these models are very flexible at handling missing data. Participants who have a missing observation are not excluded; thus, this produces the intention to treat (ITT) full information maximum likelihood (FIML) model. While missing data will be minimized through careful procedures, some missing data are inevitable with longitudinal studies. We will handle missing data using the FIML approach that is appropriate for data missing at random. We will use inclusive models with auxiliary variables related to missingness among covariates collected at baseline, if needed, to support the missing at random assumption. Multiple imputation will be considered if excessive data are missing among predictor variables, e.g., change in sleep parameters for Aim 3. Sensitivity analyses such as pattern mixture models will be employed if data are suspected to be missing not at random.

**Aim 1:** Determine the effect of Sleep-Opt, compared to a healthy living attention control group, on the primary outcomes of sleep variability, sleep duration and glycemic control (A1C).

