We will conduct MMRM using change from baseline for our primary outcome regressed onto categorical fixed effects for treatment arm, time, their interaction, and the initial baseline measure of the outcome. We will use an unstructured covariance structure to model within-person errors. If convergence problems occur, we will select the best fitting model from among several options, including random coefficients with residual covariance patterns such as autoregressive or exchangeable structure. In addition to A1C, we will estimate separate models for parameters from continuous glucose monitoring (glycemic variability, TIR). Sex will be included as a covariate and tested for moderation of the treatment effect. We will also control for BMI, A1C (for other glucose measures), and method of insulin delivery. If treatment arms are found to differ in the distribution of baseline characteristics despite randomization we will conduct sensitivity analyses including these variables as covariates. The primary endpoint will be change differences between groups at 12 weeks, based on least square means using a two-sided test with  $\alpha = .05$ . We will also assess differences in change from baseline to the 24-week endpoint to assess sustainability of effect.

**Aim 2:** Determine if Sleep-Opt will result in improved psychological and behavioral secondary outcomes, including diabetes distress, diabetes self-management behavior, and quality of life (QoL). Secondary outcomes will be analyzed with the same approach used in Aim 1.

**Aim 3:** Determine the contribution of changes in sleep variability and sleep duration during the intervention to changes in glycemic parameters (A1C, glycemic variability, TIR).

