**C.2.14 Potential Study Problems and Alternate Approaches.** **1)** Changes in diabetes treatment regimen is a potential influencer in glycemic control during the study period. The participants in the study will receive diabetes treatment per the usual care by their physicians. We will collect the modalities of treatment, changes in treatment, and totally daily insulin doses as covariates when analyzing the primary outcomes. **2)** Design consideration regarding the length of the intervention and A1C measurement: The intervention was designed for a 12-week period to achieve the best possible outcomes based on previous behavioral interventions and feedback from pilot study participants. **3)** The intervention requires smartphones; this could limit the accessibility to non-smartphone users. However, the number of smartphone users has grown significantly in the last decade. It was estimated that 77% of US adults owned a smartphone in 2016, up from 35% in 2011, making the smartphone one of the most quickly adopted consumer technologies. This number is expected to grow; thus, smartphone accessibility will become less of a limitation in the near future. **4)** Obstructive sleep apnea is screened by questionnaire and not the gold standard polysomnography in this study. It is possible that subjects with sleep apnea will be included in the study. However, this will not pose harm to the subjects, and sleep apnea and sleep duration independently contribute to glycemic control. **5.)** In our pilot study we experienced a 10% sensor failure rate. (This is less than that reported by the manufacturer and may be due to the research team's expertise in placing these devices). Most sensor failure was due to dislodgement by the participant. If dislodgement occurs, we will overnight mail a new sensor to the study participant. The dislodged

sensor will retain the recorded data. Participants will be instructed to return the sensor. We anticipate a 24 hour disruption in data collection with dislodgement.

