Convenience sampling will be used to recruit subjects throughout the Chicago metropolitan area. We expect that approximately 20% of participants will be recruited from the University of Illinois Medical Center and the remaining from the Chicago metropolitan area. This number is based on our previous study recruitment outcomes. Participants will be randomized to the intervention group or an attention control group to minimize bias. Randomization will be computer-generated in permuted blocks of 4, arranged in random order and stratified by sex. The randomization model will be developed by the study statistician ([name]) and will be executed through the REDCap data management system.

**Site/Setting.** Subjects' home is the study site. All study materials will be mailed to subjects' home and subjects and study staffs will meet via video conference for orientation to the study procedures and instruct subjects how to use the study materials. During the study period, subjects will continue to receive their usual diabetes care with their health care provider. Subjects will be encouraged to discuss any questions regarding blood glucose management with their diabetes health care provider.

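### Two different stratification schemes are stated for randomisation; if the three-factor one was run, the Aim 1 and Aim 2 models do not pre-specify all the factors used

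*Combined protocol and SAP*

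**What the plan says.** **Allocation.** Section C.2.6.1 states: "We will use permuted blocks of 4, arranged in random order and stratified by sex, A1C and age". Section 3.1 (Human Subjects Involvement, Characteristics, and Design) states: "Randomization will be computer-generated in permuted blocks of 4, arranged in random order and stratified by sex". Block size and REDCap execution are the same in both; the factors differ. No strata boundaries for A1C or age appear anywhere. The 10% A1C ceiling and the 18-65 age range in C.2.3 are eligibility limits.

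**Model.** Section C.2.10, Aim 1, specifies arm, time, their interaction, the outcome's own baseline value and sex. It then adds: "We will also control for BMI, A1C (for other glucose measures), and method of insulin delivery". For Aim 2: "Secondary outcomes will be analyzed with the same approach used in Aim 1". The Statistical Analysis Addendum keeps these models for Aims 1 and 2 and says nothing about stratification factors.

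**Rules that touch on further covariates.**
- C.2.10 foresees a data review to "identify covariates (e.g. age groups, treatment regimen) that may require statistical adjustment in the final models".
- For baseline differences between arms, Aim 1 says "we will conduct sensitivity analyses including these variables as covariates".
- C.2.14 says: "We will collect the modalities of treatment, changes in treatment, and totally daily insulin doses as covariates when analyzing the primary outcomes".
- C.2.5 says: "Analyses adjusting for the pre-treatment glucose level and other key covariates (e.g., BMI) will increase power".

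**The concern.** A reader cannot tell which factors the allocation was balanced on, and so cannot tell whether the analysis matches the design. Stratifying on a prognostic factor removes part of the chance variation in the treatment estimate. A model that leaves the factor out does not see this, so it reports a standard error larger than the true one. At stake is a small loss of precision in the reported intervals, together with a basic design fact that has two answers on record.

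**Working it through.** **1. Scheme against model.** Factors pre-specified in the model, by outcome:

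| Outcome | Sex | Age | Baseline A1C |
|---|---|---|---|
| A1C | yes | no | yes (the outcome's own baseline) |
| Sleep variability, sleep duration | yes | no | no |
| CGM measures | yes | no | yes |
| Aim 2 outcomes | yes | no | no |

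Under sex-only allocation every factor used is already in the model. Under three-factor allocation age is absent everywhere, and A1C is absent for the sleep and Aim 2 outcomes.

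**2. The plan's own figure.** C.2.5 gives 60 per group, two-sided α = 0.02, 80% power and correlations of 0.5 to 0.8. The change-score formula is (2.326 + 0.842) × √(4(1 − r)/60). It gives 0.578 SD at r = 0.5 and 0.366 SD at r = 0.8, which reproduces the stated 0.4-0.6 SD. No stratification factor enters the formula.

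**3. Plausible R².** The documents give no partial R² for age and A1C, so 0.02, 0.05 and 0.10 (jointly) are assumptions. One figure gives some anchor: section A.2 says sleep variability explained 8.2% to 15.8% of the variance in glycemic control. Assume the same A1C-sleep correlation c at baseline and week 12, with baseline-to-week-12 correlation r. The partial R² of A1C for sleep variability is then (c − cr)²/[(1 − c²)(1 − r²)]:
- c² = 0.082: 0.030 at r = 0.5 and 0.010 at r = 0.8.
- c² = 0.158: 0.063 at r = 0.5 and 0.021 at r = 0.8.

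This gives about 0.01 to 0.06, before allowing for BMI and insulin delivery.

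**4. Standard-error ratio under three-factor allocation.** If the strata categories carried all the signal and nobody were lost, model SE over true SE would be 1/√(1 − R²) = 1.010, 1.026 and 1.054. That is a ceiling. A median split of a normal variable balances only about 2/π = 0.64 of its linear signal. If a share f of those randomised is analysed, random loss leaves about f of the balance. The ratio becomes approximately 1/√(1 − 0.64 f R²):

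| Assumed R² | f = 1 | f = 120/144 | f = 120/170 |
|---|---|---|---|
| 0.02 | 1.006 | 1.005 | 1.005 |
| 0.05 | 1.016 | 1.014 | 1.011 |
| 0.10 | 1.033 | 1.028 | 1.023 |

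The 144 is the cumulative total in the timeline (Table 11); the 170 is the upper limit in C.2.3.

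**5. Simulation check.** The design was 120 randomised and 120 analysed, with blocks of 4 and two levels per factor (8 strata). The baseline-outcome correlation was 0.65, age and A1C contributed equally, and there were 60,000 trials per cell. The model had arm, baseline outcome, sex, BMI and insulin delivery. The SE ratios were 1.010, 1.015 and 1.032 (Monte Carlo SE 0.003), and the real error of a nominal 5% test was 4.7%, 4.7% and 4.4%. A separate run gave about 1.01, 1.01 and 1.04. Under sex-only allocation the ratio was 1.00 and the error 4.9-5.1%. Smaller runs with 144 randomised and 120 analysed gave about 1.00 to 1.024. At R² = 0.10 with 170 randomised, the ratio was 1.019.

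**6. What is not specific to the scheme.** From 80% power at two-sided 0.05, adding age and A1C gains 0.3, 1.5 and 3.0 points under three-factor allocation and 0.1, 1.3 and 3.2 points under sex-only. This is ordinary covariate adjustment and does not follow from the contradiction.

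**The case against.** The strongest reply is that the standard-error effect needs two conditions, not one. The three-factor scheme must have been run, and age or A1C must predict the week-12 outcome after the covariates already in the model. The documents do not establish the second condition and offer no age-outcome association. That stands, and the conclusion is conditional on both.

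A second reply is that age is not excluded, because C.2.10 names age groups as a possible adjustment. This also stands: age is not pre-specified rather than ruled out. But a stratification factor is known at randomisation and need not wait for a data review. The imbalance rule leads only to sensitivity analyses, and stratification makes imbalance on these factors unlikely. The C.2.14 covariates concern treatment. The C.2.5 remark on pre-treatment glucose could be read as meaning baseline glycemia in all three primary models, but it is ambiguous and does not override the explicit restriction in Aim 1.

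A third reply is that the size is barely resolved. At the low end the simulated ratios are within a few Monte Carlo errors of 1. If age and A1C each correlate 0.3 with BMI and insulin delivery, the ratios are 1.011, 1.006 and 1.021, which do not even rise in order. That is fair, and third decimals should not be relied on.

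A reader might infer that the mismatch biases the treatment effect, inflates type I error or undermines the sample size. None of these follows. Leaving out balanced factors makes the test conservative, and step 2 shows that the detectable difference never used them.

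**Conclusion.** The contradiction between C.2.6.1 and 3.1 is plain on the page and needs repair whichever scheme was run. If three-factor allocation was used, the Aim 1 and Aim 2 models do not pre-specify every factor that the trial randomised by.

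The numerical consequence is minor. The model standard error is roughly 0-4% too large for an assumed joint partial R² of 0.02 to 0.10, less with dropout, and nil if R² is 0 or if sex-only was run. For the A1C outcome only age is missing, so the effect there should be smaller still.

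These sizes assume two levels per factor, a linear effect of age and A1C, random dropout and a least-squares analysis at one time point. The planned repeated-measures model keeps participants with partial data, so dilution by dropout would be somewhat less than shown. The Addendum reports Bayesian credible intervals; there the counterpart is an interval that is slightly too wide. This is a point to consider, not a threat to validity.

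**What to change.** 1. Reconcile C.2.6.1 and 3.1 to the scheme actually run in REDCap.
2. If A1C and age were used, state their categories. Pre-specify age as a fixed effect in all Aim 1 and Aim 2 models, and baseline A1C in every model that lacks it: both sleep outcomes and the Aim 2 outcomes. Sex is already included.
3. If sex-only was run, correct C.2.6.1. No model change is needed to match the design; age and A1C remain optional covariates.

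The cost is wording in two protocol sections and one sentence in the analysis plan. Age is recorded at screening and A1C in the run-in before randomisation, so no new data are needed. Entered linearly, the additions take one degree of freedom for the A1C and CGM outcomes, and two for each sleep and Aim 2 outcome. Entered as categories, each factor takes its number of levels minus one.

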mg/dL), percentage of time < 70 mg/dL, and percentage of time spent  $\geq 180$  mg/dL. Interstitial glucose measurements with FreeStyle Libre and Dexcom were found to be accurate compared with capillary blood glucose reference values with a mean absolute relative difference (MARD) of 12% and 9% respectively compared to the gold standard YSI measure of blood glucose. Accuracy of 10% MARD have been approved for self-adjustment of insulin doses in clinical practice. Glycemic measures will be obtained for one week at baseline and Weeks 6, 12, and 24. In our pilot study we experienced a 10% sensor failure rate (less than 15% failure rate reported by the manufacturer and may be due to the team's expertise in placing these devices). Most sensor failure was due to dislodgement. If dislodgement occurs, we will overnight mail a new sensor to the study participant. The dislodged sensor retains the recorded data. Participants will be instructed to return the sensor. We anticipate a 24-hour disruption in data collection with dislodgement.

**C.2.9b Wrist actigraphy to measure behavioral sleep** Participants will wear an Actiwatch Spectrum Plus (Respironics, USA) on their non-dominant wrist for one week during baseline assessment, and Weeks 6, 12 and 24. Data will be collected in 30-sec epochs. Actiwatch records activity, light exposure, and wear time. Subjects will be asked to keep a daily sleep log and press an event marker on the Actiwatch at bedtime and wake-up time. Data will be downloaded and reviewed with each participant to clarify inconsistencies when the Actiwatch is returned. Rest intervals will be set using reported try-to-fall-asleep times and wake-up times on daily sleep logs or event markers if these times are missing. Using the Immobile Minutes algorithm in the Actiware 6 software, we will derive the following variables: sleep onset, sleep offset, sleep duration, sleep efficiency (a measure of sleep quality), mid-sleep time (time point between sleep onset and wake time), and standard deviation (SD) of sleep duration, an indicator of sleep variability which we previously showed to be related to glucose metabolism.

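### A single fixed block size of 4, with group-lead investigators and the project director unblinded, could let a person tracking allocations by stratum know up to a third of upcoming assignments

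*Combined protocol and SAP*

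**What the plan says.** Section C.2.6.1 (Screening, Week 0) gives the method: "We will use permuted blocks of 4, arranged in random order and stratified by sex, A1C and age". It adds that, at any time, "there will be approximately equal numbers of patients randomized to the intervention or attention control group", which implies 1:1 allocation. Section 3.1 (Human Subjects Involvement, Characteristics, and Design) describes it again with fewer factors: "Randomization will be computer-generated in permuted blocks of 4, arranged in random order and stratified by sex". Neither section gives cut-points for A1C or age, so the number of strata is unknown. In both, the random-order clause concerns how blocks or sequences are ordered. It does not say that their size varies.

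On blinding, C.2.6.1 says that "Investigators overseeing intervention and control groups and project director are unblinded" and continues in the same sentence: "for all other investigators and key personnel, randomization allocation will be concealed through blinded coding within REDCap".

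On sequence, assignment comes after the run-in and the eligibility check: "Following the 1-week run-in period and a confirmation of sleep variability" and the other criteria, "subjects will be randomly assigned to the Sleep-Opt intervention or Healthy Living attention control group". The actigraphy used in that check is described in C.2.9b: "Data will be downloaded and reviewed with each participant to clarify inconsistencies when the Actiwatch is returned". The documents do not say whether the person doing this review is blinded. Section 3.3 makes the principal investigator answerable for all subjects meeting the eligibility criteria, again without saying whether that person knows allocations.

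**The concern.** When every block has the same known size, past assignments in a stratum reveal some future ones. The fourth place in a block is always determined, and the third is determined when the first two match. Someone who knows past allocations and also has a hand in eligibility or timing could, even without intent, confirm, delay or reorder candidates according to the arm that comes next.

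The intervention is behavioral and its delivery is unmasked, so motivation and expected adherence plausibly affect sleep and A1C. The Aim 1 models in C.2.10 adjust for the baseline value of the outcome, sex, BMI, method of insulin delivery and, for other glucose measures, A1C. None of these captures selection on motivation. All three primary outcomes would be exposed to the same mechanism.

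Planned accrual is also slow. Table 11 shows two participants per arm in most enrolment months, four in all, and a sequence of that pace is easy to follow.

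**Working it through.** The documents give no predictability figure, so there is none to reproduce.

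**Inputs from the documents.** Block size 4 (C.2.6.1 and 3.1); 1:1 allocation (implied in C.2.6.1); up to 170 randomized for 120 with complete data (C.2.3).

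**Assumptions.** Number of strata from 2 (sex only) to 24, equally likely to be filled. The observer knows every earlier allocation in the participant's stratum.

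**Step 1: complete blocks of 4.** There are 6 equally likely balanced sequences. An assignment is certain when one arm has used both its places.

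| Position | P(certain) | P(best guess is right) |
|---|---|---|
| 1 | 0 | 1/2 |
| 2 | 0 | 2/3 |
| 3 | 2/6 = 1/3 | 1/3 × 1 + 2/3 × 1/2 = 2/3 |
| 4 | 1 | 1 |

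Certain share = (0 + 0 + 1/3 + 1)/4 = 33.3%. Best-guess rate = (1/2 + 2/3 + 2/3 + 1)/4 = 70.8%, against 50% by chance.

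**Step 2: unfilled last blocks.** The certain places come late in a block, so incomplete blocks lower the share. Simulated certain share:

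| Randomized | 2 strata | 8 | 12 | 18 | 24 |
|---|---|---|---|---|---|
| 120 | 32.7% | 30.6% | 29.2% | 27.1% | 25.0% |
| 170 | 32.8% | 31.4% | 30.4% | 28.9% | 27.5% |

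At 170 randomized this is about 0.275 × 170 = 47 to 0.328 × 170 = 56 participants. One third is therefore a ceiling, and 25 to 33% is the range.

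**Step 3: varied blocks.** The observer now knows the possible sizes and all past allocations in the stratum, but not the size of the current block. Sizes are drawn with equal probability, and the probability of each arm is updated after every assignment.

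| Scheme | Certain | Best guess right |
|---|---|---|
| Fixed 4 (complete blocks) | 33% | 71% |
| Random 4 or 6 | 5 to 6% | not needed here |
| Random 4, 6 or 8 | about 2% | about 67% (67 to 68% across runs) |

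A larger fixed block helps less: the certain share is 25% for size 6 and 20% for size 8.

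**Step 4: who could use the knowledge.** C.2.6.1 separates those who know allocations (investigators overseeing the groups, and the project director) from those who do not (all other investigators and key personnel). C.2.6.1 and C.2.9b leave screening and actigraphy review to study staff or to no named role, and 3.3 assigns responsibility for eligibility to the principal investigator. No section places an unblinded person in the eligibility step, and none keeps one out.

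**The case against.** The strongest reply is that the plan already conceals allocation from all other investigators and key personnel. The block size is useless to people who cannot see past assignments. If they alone handle eligibility, there is no exposure. This stands, and it limits the point to the named unblinded roles.

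A reader might infer that a third of assignments are in fact known before eligibility is confirmed. The documents do not support that. They place randomization after confirmation, and they do not say that an unblinded person screens, reviews actigraphy, signs off eligibility or triggers randomization. Under the C.2.6.1 factors, the stratum also depends on an A1C kit result from the run-in, so it is not settled at telephone screening. Under the sex-only version in 3.1 it would be. Nor do the documents show whether recruiting staff saw the block size during enrolment.

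Room for judgement is also limited. Rest intervals follow the participant's sleep log, or event markers where log times are missing. Scoring is by algorithm, and most criteria are numeric. Some discretion remains in resolving inconsistencies with the participant and in judging the wish to improve sleep.

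Finally, varied blocks barely reduce guessing, and selective enrolment needs only a better-than-chance guess. This stands too. Changing the block sizes removes near-certainty but is not sufficient alone.

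**Conclusion.** The point holds as a gap in safeguards, not as a demonstrated breach. The plan states one fixed block size of 4, leaves some leading staff unblinded, and does not keep those staff out of eligibility decisions or the timing of randomization. For an unblinded person tracking allocations by stratum, about 25 to 33% of assignments would be certain in advance. This assumes 2 to 24 equally filled strata, 120 to 170 randomized, and full knowledge of earlier allocations in the stratum. For anyone from whom allocation is concealed as planned, the figure does not apply. Whether any bias could follow turns on who confirms eligibility, which the documents leave open. Separately, C.2.6.1 and 3.1 contradict each other on the stratification factors.

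**What to change.** 1. For any assignments still to be made, generate the REDCap allocation table with block sizes varied at random within strata (for example 4, 6 and 8). Keep the sizes in a restricted statistician file and out of the text that enrolling staff use.
2. Require that actigraphy review and eligibility confirmation be completed by existing staff who are blinded to allocation, and name the role. This matters at least as much as the first step, because the best guess stays at about 67%.
3. Reconcile C.2.6.1 (sex, A1C and age) with 3.1 (sex only), and state the cut-points.

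The cost is one new allocation table and a few edited sentences. The downside is a slightly larger possible imbalance within a stratum: up to 3 or 4 inside an open block of 6 or 8, against 2 with blocks of 4. The documents do not show enrolment status. If no assignments remain, the first step is moot. The sponsor should then record who confirmed eligibility and whether they knew allocations.
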